6.1 Demographics and Baseline Characteristics

The following variables are demographic and baseline characteristics:

-Demographics (Age, Sex (male, female (premenopausal woman, postmenopausal woman)), Ethnicity, Race)

-Other baseline characteristics (weight, height, BMI, BSA, baseline glucocorticoid (i.e., hydrocortisone, prednisone, prednisolone, dexamethasone, or other), baseline glucocorticoid dose in equivalent mg of hydrocortisone/day, daily glucocorticoid dose in equivalent mg of hydrocortisone/body surface area (mg/m²), proportion of subjects with baseline glucocorticoid dose ≥ 12 mg/m²/day, baseline mineralocorticoid, baseline mineralocorticoid dose)

-Medical history

-Prior and concomitant medications

6.2 Primary Efficacy Endpoint

The primary efficacy endpoint is the overall response rate within each cohort, defined as the percentage of subjects achieving predose serum 17-OHP targets at Visit T2 (Day 29), Visit T3 (Day 57), Visit T4 (Day 85) or Visit T5 (Day 113; Amendment 2).

6.3 Secondary Efficacy Endpoints

The following are secondary efficacy endpoints:

-Androstenedione, progesterone, total testosterone, and 11-ketotestosterone levels as measured at Baseline, Visit T2 (Day 29), Visit T3 (Day 57), Visit T4 (Day 85), Visit T5 (Day 113; Amendment 2) and Follow-up Visit (Day 113 (Amendment 1) or Day 141 (Amendment 2)); and change from Baseline to Visit T2 (Day 29), Visit T3 (Day 57), Visit T4 (Day 85), Visit T5 (Day 113; Amendment 2) and Follow-up Visit (Day 113 (Amendment 1) or Day 141 (Amendment 2)).

-Serum 17-OHP levels as measured at Visit T1 (Day 1), Visit T2 (Day 29), Visit T3 (Day 57), Visit T4 (Day 85), and Visit T5 (Day 113; Amendment 2) at h0, h1, h2, h3 and h4 (predose and 1-4 hours after administration of the morning replacement glucocorticoid, mineralocorticoid (if applicable), and/or study drug (if applicable) doses); and change from baseline (Visit T1 (Day 1)) to Visit T2 (Day 29), Visit T3 (Day 57), Visit T4 (Day 85), Visit T5 (Day 113; Amendment 2).

-Salivary 17-OHP levels as measured at Visit T1 (Day 1), Visit T2 (Day 29), Visit T3 (Day 57), Visit T4 (Day 85), and Visit T5 (Day 113; Amendment 2) (at time points h0, h2 and h4 (just before, 2 hours after, and 4 hours after (respectively) administration of the morning replacement glucocorticoid (if applicable), mineralocorticoid (if applicable) and/or study drug (if applicable) doses)) and change from Baseline (Visit T1 (Day 1)) to Visit T2 (Day 29), Visit T3 (Day 57), Visit T4 (Day 85), and Visit T5 (Day 113; Amendment 2).

6.4 Safety Endpoints

The following are safety endpoints:

-Incidence of (serious) adverse events

-Serum and urine pregnancy test results

-Vital signs (weight, blood pressure (systolic, diastolic), pulse rate, respiratory rate, body temperature); and change from baseline in vital signs

-Physical examination (interpretation)

-Electrocardiogram parameters (heart rate, P-R interval, QRS interval, Q-T interval, QTcF interval, R-R interval, overall interpretation); and change from baseline in ECG parameters

-Laboratory values and change from baseline in laboratory values, including:

-Hematology (hematocrit, hemoglobin, platelets, red blood cells, white blood cells, neutrophils, eosinophils, basophils, lymphocytes, monocytes)

-Clinical chemistry (serum albumin, alkaline phosphatase, ALT (SGPT), AST (SGOT), blood urea nitrogen, calcium, creatinine, plasma glucose, total bilirubin, total serum protein, magnesium, sodium, potassium, chloride, bicarbonate)

-Coagulation parameters (prothrombin time (PT), aPTT, INR)

-Blood hormones (ACTH and cortisol)

-Saliva hormones (progesterone (premenopausal women only), cortisol)

-Urinalysis (bilirubin, glucose, ketones, white blood cells, nitrite, blood, pH, protein, specific gravity, urobilinogen)

-Urine microscopy (clarity, color, RBC, WBC, bacterial count, squamous epithelial cells, renal tubular cells, transitional cells, hyaline casts, granular casts, RBC casts, WBC casts, triple phosphate crystals, calcium carbonate crystals, calcium oxalate crystals, urate salts, uric acid crystals, yeast cells, molds, mucus, amorphous phosphates)

6.5 Pharmacokinetic Variables

Pharmacokinetic and pharmacodynamic parameters will be determined based on the concentrations of nevanimibe HCl and its major metabolite(s). A list of pharmacokinetic and pharmacodynamic parameters of interest can be found in section 7.8.

6.6 Other Variables

The following additional variables are related to exposure and compliance:

-Duration of treatment (number of patient years per dose)

-Duration of exposure (average number of days of treatment per subject)

-Compliance (percentage of expected study drug taken)

7. Statistical Analysis Methods

All summarizations will be performed in an exploratory manner only. Where applicable and meaningful, analyses will be performed by cohort, nevanimibe HCl dose or study visit, and overall.

7.1 Descriptive Statistics

The default summary statistics for quantitative variables will be the number of non-missing observations (n), mean (arithmetic or geometric (if applicable for pharmacokinetic data)) and/or median, standard deviation (SD) and/or quartiles (Q1 and Q3), minimum (min) and maximum (max) for those patients with data available.

For qualitative variables, the number (n) and percentage (%) of patients with non-missing data per category will be the default summary presentation, and where appropriate and present, the number of missing values as a “Missing” category. Percentages will be calculated using a denominator of all patients in a specified population or treatment group. The denominator will be specified in a footnote to the tables for clarification if necessary.

7.2 Rounding Rules

7.2.1 Estimates of the Mean and Standard Deviation

When using raw data, the mean will be presented to 1 more decimal place and standard deviation will be presented to 2 more decimal places than the raw data. Consequently, these parameters will be calculated to at least 1 more decimal place than will be presented, and the result will be rounded to obtain the presented value.

7.2.2 Other Data

Quartiles, confidence intervals (CIs) and median will be presented with the same number of decimal places as the mean. Minimum and maximum will be presented with the same number of decimal places as the data used. For estimates of proportions, the result will be rounded to 3 decimal places. If proportions are displayed as percentages, 1 decimal place will be displayed. For example, a proportion of 0.655 will be presented in percentage form as 65.5%.

7.3 Calculation of Study Days and Durations

Study days and, if applicable and meaningful, durations will be determined by comparing the respective date to the date of first dose of study drug.

- If the respective date is on or after date of first dose of study drug:
$$\text{Study day/Duration} = (\text{Date (e.g., date of visit)} - \text{Date of first dose of study drug}) + 1$$
- If the respective date precedes the date of first dose of study drug:

Study day/Duration = Date (e.g., date of medical history event) - Date of first dose of study drug

Time to onset and duration of adverse events will be calculated as follows:

- Time to onset = start date of AE - date of first dose of study drug [+1 for AE starting on or after date of first dose of study drug]
- Duration of adverse event = (stop date - start date) + 1

7.4 Evaluation of Demographics and Baseline Characteristics

7.4.1 Disposition of Patients

Subject disposition will be tabulated including the numbers of screened subjects, subjects completing the study, subjects withdrawing from the study, and subjects in the mITT population, PPP, SP and PKP. Subjects withdrawn from the study will be listed along with the primary reason for withdrawal. COVID-19 relatedness of early study terminations will be tabulated separately. In addition, the primary reason for withdrawal will be tabulated. Exclusion from analysis sets as well as the reason(s) for exclusion will be listed.

7.4.2 Demographics

Demographic information (age, sex (including information on menopause), ethnicity, race) will be summarized using summary statistics (N, mean, SD, median, minimum, maximum, upper and lower quartile) for continuous variables (age) or absolute and relative frequencies (n, %) for categorical variables (sex, ethnicity, race). Results will be presented for each analysis population (mITT, PPP, SP, PKP), by cohort and overall. Additionally, baseline characteristics will be presented for the SP population for the male and female subgroups.

7.4.3 Baseline Characteristics

Baseline characteristics (height, weight, BMI, BSA, type of baseline glucocorticoid (i.e., hydrocortisone, prednisone, prednisolone, dexamethasone, or other), baseline daily glucocorticoid dose in equivalent mg of hydrocortisone/day, baseline daily glucocorticoid dose in equivalent mg of hydrocortisone/body surface area (mg/m²), proportion of subjects with baseline glucocorticoid dose ≥ 12 mg/m²/day, baseline mineralocorticoid, baseline mineralocorticoid dose in μ g of fludrocortisone, and baseline fold-ULN for 17-OHP) will be summarized using summary statistics for continuous variables and absolute and relative frequencies (n, %) for categorical variables. Results will be presented for the mITT population and the SP, by cohort and overall. Additionally, they will be presented for the SP population on the male and female subgroups.

Conversion of glucocorticoid dose to equivalent mg of hydrocortisone will be performed using conversion factors listed below (updated with global amendment 2 for all data analyses):

Glucocorticoid	Equivalent Doses (mg)	Conversion Factor	Equivalent mg Hydrocortisone
Hydrocortisone	20	1	20
Prednisone	4	5	20
Prednisolone	4	5	20
Dexamethasone	0.25	80	20

Conversion of mineralocorticoids into µg of fludrocortisone will be performed using conversion factors listed below:

Mineralocorticoid	Equivalent Doses Mineralocorticoid Activity (mg)	Conversion Factor	Equivalent µg Fludrocortisone
Hydrocortisone	20	0.005	100
Prednisone	50	0.002	100
Prednisolone	50	0.002	100
Dexamethasone	-	0	0
Cortisone acetate	25	0.004	100
Fludrocortisone	0.1	1	100

BMI will be calculated using the following formula:

$$BMI = \frac{\text{weight [kg]}}{\text{height}^2[\text{m}^2]}$$

BSA will be calculated according to Dubois and Dubois using the following formula:

$$BSA = 0.007184 \times (\text{height [cm]})^{0.725} \times (\text{weight [kg]})^{0.425}$$

In addition, for Cohort 2, the type of glucocorticoid, daily glucocorticoid dose in equivalent mg of hydrocortisone/day, daily glucocorticoid dose in equivalent mg of hydrocortisone/body surface area (mg/m²), and the proportion of subjects with glucocorticoid dose ≥12 mg/m²/day will be summarized for Visit S1 (the initial screening visit), Visit S2, Visit B1, and Visit T1.

7.4.4 Medical History and Prior and Concomitant Medication

Absolute and relative frequencies (n, %) of medical history will be described based on MedDRA system organ class (SOC) and preferred term (PT) levels for the SP, overall.

Absolute and relative frequencies (n, %) of prior and concomitant medications (separately) will be provided based on Anatomical Therapeutic Chemical (ATC) Classification code levels 1 through 5 for the SP, overall.

7.5 Evaluation of the Primary Efficacy Endpoint

The primary efficacy endpoint, the percentage of subjects achieving predose serum 17-OHP targets at Visit T2 (Day 29), Visit T3 (Day 57), Visit T4 (Day 85), or Visit T5 (Day 113; Amendment 2), will be evaluated for the mITT population and repeated for the PPP. Achievement of the serum 17-OHP targets will be determined as follows:

-Men and postmenopausal women: 17-OHP $\leq 2 \times$ ULN

-Premenopausal women:

-Follicular phase: 17-OHP $\leq 2 \times$ follicular phase ULN

-Luteal phase: 17-OHP $\leq (2 \times \text{follicular phase ULN} + (\text{luteal phase ULN} - \text{follicular phase ULN}))$

Each subject who falls below the applicable 17-OHP target for at least one visit will be counted as a responder to treatment with nevanimibe HCl. Any subjects who prematurely terminates the study and was not categorized as responder before termination will be counted as a non-responder. The responder rate will be calculated overall and for each cohort (Cohort 1 and Cohort 2), by nevanimibe dose and overall. The clinical trial will be regarded as successful if a responder rate of at least 40% was observed for either of the two cohorts.

The 90% exact binomial confidence interval will be calculated for the responder rates. A variation of the following SAS code will be used for calculation of the confidence limits:

```
proc freq data = input-dataset;  
    tables responder / binomial(level='Yes' wilson) alpha=.1;  
    by visit;  
    exact binomial;  
    ods output BinomialCLs = output-dataset;  
run;
```

Additional summary statistics will be prepared, including summaries relative to the upper limit of normal (\times ULN) and absolute as well as relative change from baseline. The dose-response relationship may additionally be displayed graphically.

7.6 Evaluation of Secondary Efficacy Endpoints

All secondary variables will be evaluated for the mITT population and the PPP.

Absolute values as well as change and percentage change from baseline in androstenedione, progesterone, total testosterone, and 11-ketotestosterone (as available) as measured at Visit T2 (Day 29), Visit T3 (Day 57), Visit T4 (Day 85), Follow-up Visit (Day 113; Amendment 1) or Visit T5 (Day 113; Amendment 2) and Follow-up Visit (Day 141; Amendment 2) will be assessed descriptively using summary statistics for continuous variables. Percentage change from baseline at Day x will be calculated as $(\text{measurement at Day } x - \text{measurement at baseline}) / (\text{measurement at baseline})$. Results will be presented overall and by cohort. Levels of androstenedione, testosterone and 11-ketotestosterone will additionally be summarized by sex (male, female) and cohort (cohort 1, cohort 2).

Absolute values as well as change and percentage change from baseline in serum 17-OHP levels at Visit T1 (Day 29), Visit T2 (Day 57), Visit T3 (Day 85), Visit T5 (Day 113; Amendment 2) and Follow-up Visit (Day 113 (Amendment 1) or Day 141 (Amendment 2)) will be evaluated by cohort, nevanimibe dose and overall. For each study visit, up to five (5) samples are collected per subject at specified pre/postdose timepoints. For each study day, the sum of all values from the time series (i.e., samples at specified pre/post-dose time points) will be calculated and used for comparison with data from Visit T1. Percentage change from baseline at Day x will be calculated as $(\text{measurement at Day } x - \text{measurement at baseline}) / (\text{measurement at baseline})$. For those samples with a 17-OHP value $>30 \mu\text{g/L}$, the undiluted value received after transformation of the measurement after appropriate dilution will be used. A footnote detailing the number of samples that exceeded the measurement limit of $30 \mu\text{g/L}$ will be included.

Results will be described using summary statistics for continuous variables. 90% confidence limits will be calculated for each of the visits.

Change and percentage change from Baseline (Visit T1 (Day 1)) in salivary 17-OHP levels (samples collected on-site) at Visit T2 (Day 29), Visit T3 (Day 57), Visit T4 (Day 85), and Visit T5 (Day 113; Amendment 2) will be evaluated by cohort, nevanimibe dose and overall. For each sampling day, up to five (5) different time points are collected per subject. Summary statistics for each time point will be calculated for each sampling day and used for comparison with data from Visit T1. In addition, for the five (5) on-site salivary samplings, the sum of the h0, h1, h2, h3 and h4 values per subject per study day will be evaluated by cohort, nevanimibe dose and overall, for all subjects with data available at all five timepoints for the respective on-site sampling day. Availability of data for imputation of the missing values will be assessed during the final DRM meeting prior to data analysis, and changes may be made to the described analysis to utilize all available data more effectively. Results will be described using summary statistics for continuous variables.

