4.2. Inclusion Criteria

Each subject must meet all the following criteria to be enrolled in this study:

1. Provision of signed and dated informed consent prior to any study-specific procedures
2. Men and women 18 to 80 (70 in the Czech Republic) years of age (inclusive) at the time of informed consent
3. Documented historical diagnosis of classic CAH due to 21-hydroxylase deficiency based on either or both of the following criteria:
 - Documented genetic mutation in the CYP21A2 enzyme consistent with a diagnosis of classic CAH
 - Historical documentation of elevated 17-OHP (e.g., in infancy or following a cosyntropin/ACTH stimulation test)
4. Serum 17-OHP \geq 4x ULN during the Baseline Period
 - Premenopausal women in the follicular phase of the menstrual cycle must have serum 17-OHP \geq 4x follicular phase ULN
 - Premenopausal women in the luteal phase of the menstrual cycle must have serum 17-OHP \geq (4x follicular phase ULN + (luteal phase ULN – follicular phase ULN))
5. Chronic glucocorticoid replacement therapy for at least 6 consecutive months prior to Screening
6. Stable glucocorticoid and mineralocorticoid regimen for at least 4 weeks prior to the Screening (S1), Baseline (B1), and Enrollment (T1) Visits
7. For subjects who undergo maintenance glucocorticoid dose adjustment between Screening and Enrollment, stable serum 17-OHP levels (adjusted as needed for menstrual cycle phase) prior to Enrollment, defined as the most recent 2 values being within 30% of each other (calculated as $100 \times (1 - (\text{smaller value}/\text{larger value}))$)
8. Female subjects of childbearing potential must consent to use two medically acceptable methods of contraception, excluding depot progesterone, throughout the study period and for 30 days after the last dose of study treatment during any sexual intercourse with a fertile male partner (in France: Fertile subjects (male and female) must consent to use two medically acceptable methods of contraception, excluding depot progesterone, throughout the study period and for 30 days after the last dose of study treatment during any sexual intercourse with a fertile partner of the opposite sex)

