7.2.1. Visit B1 (Day -14; Week -2)

Prior to Visit B1, the Investigator should review whether the subject continues to be eligible for the study. If not, the subject should be screen-failed from the study. Please note that the Screening serum cortisol level result does not need to be available for the subject to proceed with Visit B1.

At Visit B1, appropriate study site personnel should:

- Record AEs and update medications.
- Record the date and time of the subject's last dose of glucocorticoid prior to the visit.
- Record vital signs and weight.
- Within 30 minutes prior to administration of morning replacement glucocorticoid and mineralocorticoid (if applicable) doses, collect blood samples for hormones (17-OHP, P, cortisol, A4, ACTH, total testosterone, and 11-ketotestosterone), and collect saliva samples for 17-OHP, P, and cortisol.
 - For each study visit, the first hormone sample collection that is obtained at the study site should be done between 6-10 AM (06:00-10:00), as close to 8 AM (08:00) as practicable.
 - Hormones should not be collected if the subject already took their replacement glucocorticoid and/or mineralocorticoid dose that morning; instead, the sample collection should be rescheduled for the next day or as soon as is feasible.

- For female subjects of childbearing potential only, collect a urine sample and perform a urine pregnancy test.
- Instruct the subject on the use of the eDiary for recording glucocorticoid, mineralocorticoid, and/or study drug doses. If needed, provision a device for accessing the eDiary.
- If the subject is a premenopausal woman, instruct her on the use of the eDiary for recording the start date of her last menstrual period, and ask her to record the start date of her last menstrual period using the eDiary.
- Ask the subject to self-administer their morning replacement glucocorticoid and mineralocorticoid (if applicable) doses.
- Ask the subject to record the time of glucocorticoid and mineralocorticoid (if applicable) administration using the eDiary.
- Remind the subjects to collect a salivary 17-OHP profile within approximately one week prior to the next study visit (Visit T1).
- Schedule the next study visit (Visit T1).

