LLT	Lowest level term
MC	Mineralocorticoid
max	Maximum
MedDRA	Medical Dictionary for Regulatory Activities
min	Minimum
mITT	modified Intention-to-Treat population
N	Number of subjects
n	Number of non-missing observations
P	Progesterone
PK	Pharmacokinetic
PKP	Pharmacokinetic population
PPP	Per protocol population

PT	Preferred term
Q1	First quartile
Q3	Third quartile
SAP	Statistical analysis plan
SAE	Serious adverse event
SAS®	Statistical Analysis System
SD	Standard deviation
SP	Safety population
SOC	System organ class
T	Testosterone
TEAE	Treatment-emergent adverse event
TFLs	Tables / figures / listings
ULN	Upper limit of normal

1. Introduction

This statistical analysis plan (SAP) contains a more technical and detailed elaboration of the principal features of the statistical analyses as described in the Study Protocol of the ATR-101-202 study (global protocol amendment 2) dated 31-MAY-2019 and includes detailed procedures for executing the statistical analysis of the primary and secondary variables and other data. The SAP is finalized and signed prior to final database lock at the end of the study. 17-OHP level cutoffs and targets are adjusted per protocol for menstrual cycle phase for premenopausal women.

2. Study Design and Objectives

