3.2 Coding Systems and Conventions

3.2.1 Definition of Baseline

In general, all values recorded at Visit T1 (Day 1) prior to the first dose will be regarded as baseline values for this study. In case no predose Visit T1 (Day 1) value was recorded (expected for ECG and for coagulation parameters), the most recent value prior to Visit T1 (Day 1) will be used as baseline value instead.

For serum or plasma 17-OHP, P, cortisol, A4, ACTH, total T, and 11-ketoT, baseline is defined as the mean of the predose value from Visit T1 (Day 1) and the most recent “0-hour” value prior to Visit T1 (Day 1), if the glucocorticoid dose was the same as at Visit T1 (Day 1) (if not the same, then only the predose Visit T1 (Day 1) value will be used).

For on-site salivary 17-OHP, P, and cortisol, baseline is defined as the mean of the predose value from Visit T1 (Day 1) and the most recent “0-hour” value prior to Visit T1, if the glucocorticoid dose was the same as at Visit T1 (if not the same, then only the predose Visit T1 value will be used). Change from baseline will be calculated for salivary 17-OHP values obtained 30 minutes before, as well as 2 hours and 4 hours after intake of the morning dose of nevanimibe HCl. For additional analyses, baseline for on-site salivary 17-OHP is further categorized by the time of sample relative to the time of the morning dose of nevanimibe HCl. Thus, baseline for the predose measurement on visits T2/T3/T4/T5 is defined for the additional analyses as above, while it is defined as the T1 sample taken 2 hours after the morning dose of nevanimibe HCl for the T2/T3/T4/T5 sample taken 2 hours after the morning dose, and defined as the T1 sample taken 4 hours after the morning dose for the T2/T3/T4/T5 sample taken 4 hours after the morning dose.

For home collection salivary 17-OHP profiles, baseline for the 8 AM (08:00), noon (12:00), 4 PM (16:00), 8 PM (20:00), and 10-11 PM (22:00-23:00) time points is defined as the value obtained for the corresponding time point at Day -8.

Except for the above-mentioned case, all values recorded after the first treatment with the study drug will be regarded as post-baseline values.

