4.2 Subgroups

Two cohorts (Cohort 1 and Cohort 2) are included in this trial. Eligible subjects are assigned to Cohort 1 if their serum 17-OHP is $\geq 4x$ ULN at the initial screening visit. If this is not the case, subjects may undergo a reduction in glucocorticoid dose and will be reassessed for their serum 17-OHP value. If the serum 17-OHP level is $\geq 4x$ ULN after reassessment, the subject can be enrolled into Cohort 2. No formal group sizes have been appointed for Cohort 1 and 2. All efficacy and PK analyses will be performed overall and by cohort.

Additionally, levels of androstenedione, testosterone and 11-ketotestosterone will be summarized by sex (male, female).

To assess the possible impact of protocol amendment 2 on the safety profile, the analysis of adverse events will be repeated for the subgroup of subjects enrolled according to global amendment 1 and global amendment 2.

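### Serum progesterone, a secondary efficacy endpoint, is pooled over men and pre- and postmenopausal women with no handling of cycle phase, so its mean change can partly reflect ovarian cycling

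*SAP*

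**What the plan says.** SAP 6.3 lists the steroid endpoints together: "Androstenedione, progesterone, total testosterone, and 11-ketotestosterone levels as measured at Baseline", with change from baseline to each later visit and to follow-up. For these hormones SAP 7.6 states "Results will be presented overall and by cohort". Protocol 9.5.2.1 adds a breakdown by nevanimibe dose. The planned Table 14.2.4 names only the visit in its title.

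The by-sex summary appears twice and leaves progesterone out both times. SAP 4.2 has "levels of androstenedione, testosterone and 11-ketotestosterone will be summarized by sex (male, female", and SAP 7.6 has "Levels of androstenedione, testosterone and 11-ketotestosterone will additionally be summarized by sex (male, female) and cohort (cohort 1, cohort 2". Progesterone is the only one of the four steroids grouped in SAP 6.3 that is not named.

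The population is mixed: "Men and women 18 to 80 (70 in the Czech Republic) years of age (inclusive) at the time of informed consent" (Protocol 4.2). SAP 6.1 and 7.4.2 record menopausal status. Cycle phase is handled for one hormone only: "17-OHP level cutoffs and targets are adjusted per protocol for menstrual cycle phase for premenopausal women" (SAP 1). Salivary progesterone, by contrast, is restricted to premenopausal women (Protocol Table 3, SAP 6.4). Protocol 6.6 has premenopausal women enter period start dates in the eDiary, partly so that cycle phase can be judged.

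**The concern.** The secondary objective is change in adrenal steroids and their intermediates. Protocol 1.1 names progesterone as a substrate of the deficient enzyme, so it is a reasonable adrenal marker. In men and postmenopausal women its serum level can be read mainly that way. In women who ovulate it also carries ovarian output, which varies over the cycle. The plan recognises this kind of problem for 17-OHP, which has separate follicular and luteal limits, but does nothing comparable for serum progesterone.

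There is no control arm, so nothing in a pooled change separates the two sources. With about 20-24 subjects, a few women sampled in a different phase at a later visit can pull the mean change up or down. At stake is how one secondary readout is interpreted.

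**Working it through.** The documents give no figure for this endpoint and Protocol 9.2 reports no formal sample size calculation, so there is no planned number to reproduce. Two illustrations show whether the mechanism is possible and how far its size depends on assumptions.

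**1. Does the 28-day visit spacing hold phase constant?** T2 (Day 29) is 28 days after T1 and T5 (Day 113) is 112 days after T1. Take a woman at cycle day 8 at T1 (assumed) with a regular cycle of L days (assumed). Her cycle day is (8 + 28) modulo L at T2 and (8 + 112) modulo L at T5.

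| L (days) | T2: 36 mod L | T5: 120 mod L |
|---|---|---|
| 25 | 11 | 20 |
| 27 | 9 | 12 |
| 28 | 8 | 8 |
| 29 | 7 | 4 |
| 31 | 5 | 27 |
| 32 | 4 | 24 |

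With cycles of 27-29 days she stays in the first half throughout. With 25, 31 or 32 days she has reached the second half by T5, but at T2 she is still early in the cycle. The schedule therefore limits drift for some women and not for others. The visit window of ±2 days and the re-anchoring allowed by Protocol 6.1 add some variation.

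**2. How many women would cancel a true adrenal fall in the pooled mean?** All inputs except the upper planned size of 24 are assumed, in arbitrary units:
- n = 24 subjects.
- E = luteal excess of 5 to 20 units.
- A = adrenal progesterone before treatment of 1, 4 or 10 units, halving on treatment.

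The true fall in the mean is A/2. Each woman who is follicular at baseline and luteal at the visit raises the mean change by E/n: 5/24 = 0.21 to 20/24 = 0.83. The number needed to cancel the fall is k = (A/2)/(E/n) = 12A/E, rounded up.

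| A | True fall A/2 | k at E = 20 | k at E = 5 |
|---|---|---|---|
| 1 | 0.5 | 0.6, so 1 | 2.4, so 3 |
| 4 | 2 | 2.4, so 3 | 9.6, so 10 |
| 10 | 5 | 6 | 24 |

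The range is 1 to 24 women, and k is a net count: a woman moving from luteal to follicular offsets one moving the other way. In a by-cohort table each woman weighs more. With an assumed 12 per cohort, her contribution doubles and k = 6A/E.

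**The case against.** The strongest reply concerns size. A reader might infer that one to three women would be enough to hide the drug's effect. That holds only in the row with A = 1, and the documents point to higher adrenal levels. Protocol 1.1 describes precursors accumulating before the enzyme block, entry requires 17-OHP of at least 4 times ULN, and the earlier Phase 2 study had a mean of 53 times ULN (Protocol 3.2). Those multiples are for 17-OHP and do not give a progesterone level, but they make the lowest row hard to defend as the typical case.

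Other points also stand:
- The number of ovulating women is unknown. Women of childbearing potential must use two contraceptive methods, with only depot progesterone excluded, and Protocol 1.1 mentions secondary polycystic ovary syndrome. Either could reduce the effect.
- SAP 7.1 allows medians, quartiles and ranges, and Listing 16.1.2.4 shows individual values. A few women would move a median little. However, SAP 7.1 offers mean and/or median, so the median is not assured, and a listing does not correct a summary.
- A reader might infer that the secondary objective cannot be met. It can: serum and salivary 17-OHP, androstenedione, testosterone and 11-ketotestosterone also serve it.
- A reader might also take omission from the by-sex split to be the whole defect. Adding progesterone to that split would still pool pre- and postmenopausal women, and cycle phases, among the women.

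None of this answers the textual point that no rule for menopausal status or cycle phase applies to serum progesterone.

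**Conclusion.** The gap is real and minor. As written, the pooled progesterone change mixes an adrenal signal with an ovarian one, and the trial has no control arm to separate them. Its size cannot be derived from the documents, because the adrenal level, the luteal excess, cycle lengths and the number of ovulating women are all unstated. Under the assumptions shown, the count of women needed to cancel a halving runs from 1 to all 24, so the illustration supports a possible distortion and not a likely or large one. Fewer ovulating women, or reliance on medians, would reduce it.

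Protocol 9.5.1.2 sets no targets for secondary endpoints and SAP 7 calls all summaries exploratory. The 40% responder rule, which uses phase-adjusted 17-OHP, is unaffected.

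**What to change.** In SAP 4.2, SAP 7.6 and Table 14.2.4:
- Summarise serum progesterone for men plus postmenopausal women as the main adrenal display, and for premenopausal women separately, with medians in both.
- For premenopausal women, show change from baseline only where the baseline and visit samples fall in the same cycle phase. If that leaves very small cells, flag mismatches in Listing 16.1.2.4 instead of tabulating them. Grouping by phase at the visit alone is not enough, because a woman who was follicular at baseline would remain confounded inside the luteal group.
- State how phase is assigned to baseline. Under SAP 3.2.1 "baseline is defined as the mean of the predose value from Visit T1 (Day 1" and the latest earlier 0-hour value, if the glucocorticoid dose is unchanged. That earlier sample may come from "Visit B1 (Day -14; Week -2" (Protocol 7.2.1), which in an assumed 28-day cycle is half a cycle from T1. The matching rule must say what happens when the two baseline samples differ in phase.
- Keep the pooled table as supportive.

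The cost is one more split of a planned table, and some small cells. Menopausal status and period dates are already collected, and SAP 2.11 provides for amendment before final database lock.
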